The Study Group, which consists of all site investigators, participating harvesters, and research coordinators, will meet annually to discuss the progress of the study and any problems encountered during the conduct of the trial.

B. Monitoring Subject Safety

The Perry Point CSPCC and CSPCRPCC will provide summaries of all serious adverse events reported to the Study Chairman and DMC at least twice a year.

C. Monitoring Subject Intake and Probation or Termination of Participating Sites

The Study Chairman and the Study Biostatistician will monitor the intake rate and operational aspects of the study. Participating medical centers will continue in the study only if adequate subject intake is maintained. The Executive Committee may take action leading to the discontinuation of subject enrollment at a center with the concurrence of the CSPCC Director. If recruitment is not proceeding at an appropriate rate, the Study Chairman and Study Biostatistician will

scrutinize the reasons for inadequate subject participation. Based on this information, the Executive Committee may choose to drop centers or add additional centers. The DMC and Director of CSRD will be notified regarding the dropping or adding of centers. Participating sites that do not enroll at least 24 subjects during the first 12 months of the study will be placed on probation and given an opportunity to improve within a reasonable period. After the first 12 months, participating sites that do not reach 75% of enrollment target during any six-month evaluation time will be placed on probation and given an opportunity to improve within a reasonable period. If a medical center is placed on probation, the Study Chairman will confer with the site personnel and visit the site, if necessary, to help improve the rate of recruitment. If there is no improvement in accrual during the probation period, the site may be subject to reduced funding or possible termination as a study site. To plan for the possible termination of a site(s) and the addition of a new site(s), back up sites with IRB approval will be identified prior to study initiation to minimize the delay in adding a new site. The Executive Committee will only take actions leading to discontinuation of a center with the concurrence of the CSPCC Director. If a center is terminated from the trial, resources will be reallocated to other centers or used to start up a backup site.

D. Alternate Plan if Recruitment Goals are not Met

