16 SITES

	3 Month Start Up FY 13	Recruitment 12 months FY14	Recruitment 12 months FY 15	Recruitment 12 months FY 16	12 months F/U FY 17	3 months close out FY 18	
Research Coordinator GS 11 1.00 FTE	\$25,045.00	\$105,190.00	\$110,450.00	\$115,972.00	\$121,771.00	\$31,965.00	\$510,393.00
SALARY TOTAL	\$25,045.00	\$105,190.00	\$110,450.00	\$115,972.00	\$121,771.00	\$31,965.00	\$510,393.00
Supplies	\$1,500.00	\$1,500.00	\$1,500.00	\$1,500.00	\$1,500.00	\$0.00	\$7,500.00
IT Equipment	\$2,000.00	\$150.00	\$150.00	\$150.00	\$150.00	\$0.00	\$2,600.00
Patient Payment			\$3,600.00	\$3,600.00	\$3,600.00	\$0.00	\$10,800.00
Annual Travel Meetings \$1,000 per person	\$3,000.00	\$3,000.00	\$3,000.00	\$3,000.00	\$3,000.00	\$2,000.00	\$17,000.00
GRAND TOTAL SUPPLIES/TRAVEL	\$31,545.00	\$109,840.00	\$118,700.00	\$124,222.00	\$130,021.00	\$33,965.00	\$548,293.00

CSP#588 REGROUP
SITE (RESEARCH COORDINATOR) BUDGET
36 Months Recruitment
ONE YEAR FOLLOW-UP
August 16, 2012
BASED ON 2 PATIENTS ENROLLED PER MONTH PER SITE

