2.2 Endpoints

2.2.1 Primary Outcome Measures

The primary outcome measure is MACE following randomization and the index CABG.

For hypothesis 1: The outcome measure, MACE (major adverse cardiac events) is a composite endpoint that includes death (all-cause), myocardial infarction (MI), and revascularization for myocardial ischemia. Each randomized participant (either in EVH or OVH) will be followed after the index CABG to capture the time-to-MACE event where an ‘EVENT’ will be defined as either death (all-cause) or an MI or a revascularization procedure during the follow-up period. Total follow-up period will be 6.5 years of which the first 4.5 years will be active follow-up (using in-clinic visit or by telephone) period and will be carried out by the site personnel. The remaining 2 years will be passive follow-up which will be carried out centrally by the chair’s office staff using VA clinical and administrative databases (CPRS, VASQIP, etc.). A minimum of 1 year of active follow-up will be used for participants who will be randomized at the tail end of the 3-year projected enrollment period of the study. The participants who will either be lost to follow-up or will not experience an ‘EVENT’ before the end of the follow-up period will be considered as right-censored. The primary analysis of such time-to-Mace event data will include the events only from the active follow-up period (which is approximately 4.5 years).

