3.6 Sample Size

In the ROOBY study (CSP # 517) (Shroyer et al. 2009), 1-year MACE rates were 9.9% in the OVH group and 15.3% in the EVH group ($p=0.0025$). The executive committee for the REGROUP study assumed that during the REGROUP study, 15.5% of the participants in the EVH group will experience MACE in the first year post surgery. The committee also expects a 6 percentage point improvement in the 1-year MACE rate in the OVH group.

To detect the expected 6 percentage point difference in 1-year MACE rates between EVH (15.5%) and OVH (9.5%), a sample size of 545 in each group will be required at 85% power, 5% type-I error rate and with a two-sided test. Since, it would be possible to capture the majority of the MACE from the VA databases even if participants drop out before the one-year clinic visit, a relatively small inflation factor of 5% is used to inflate the sample size to account for the drop-outs. Thus, a total of 1,150 participants need to be randomized in the study to achieve the said power.

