6.6.2 MACE by EVH Experience

The rate of MACE and its components (all-cause mortality, nonfatal myocardial infarction, & repeat revascularization) will be reported by harvesters' EVH Experience: > 100 but < 500, > 500 but < 1,000, > 1,000 but < 2,000, and >2,000 endoscopic vein harvests completed. A separate table (similar to TABLE 21) will be provided for each level of experience.

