7 STATISTICAL ANALYSES

7.1 Primary Outcome

The primary objective of this study is to investigate the impact of SVG harvesting techniques – OVH vs. EVH on MACE, a composite end point of all-cause mortality, nonfatal myocardial infarction and repeat revascularization, over the active follow-up period of the study postoperatively. The active follow-up time would begin with the first randomized patient and end after the last participant randomized has reached at least one-year of follow-up. Assuming the enrollment period is approximately three years, this would equate to approximately 4 to 4.5 years of active follow-up (in-clinic visit or contact by telephone carried out by site personnel), which will also be followed by two years of passive follow-up (carried out centrally by the chair's office staff using VA administrative databases). Thus, total follow-up time (active and passive) would be approximately 6.5 years. The primary outcome in the study is time (from index CABG surgery date) until the event of interest, MACE, or time-to-MACE during active follow-up (~4.5 years). Only the first event among participants will be considered as the MACE event.

To begin the analyses, the rate of MACE and its components (all-cause mortality, nonfatal myocardial infarction, & repeat revascularization) during active follow-up will be reported, both collectively and by SVG harvesting technique, OVH vs. EVH, considering only the first event so that components sum to total MACE (similar to TABLE 21). Survival analysis techniques will be employed to analyze the time-to-MACE data. Participants who are either lost-to-follow-up or did not experience a MACE event during the active follow-up period will be considered right-censored. Kaplan-Meier nonparametric survival estimates for risk of MACE will depict the unadjusted impact of SVG harvesting technique on MACE (FIGURE 2). Survival time represents time not experiencing a MACE. Tests of

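### MACE by harvester experience is tabulated as crude percentages over unequal follow-up, so experience levels enrolled at different times can differ with the same true hazard

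*SAP*

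**What the plan says.** Objective 6 (SAP 2.1) is to determine the role of harvester experience in clinical outcomes. It is exploratory with no hypothesis, and SAP 2.2.2 names MACE as its measure. The dedicated outputs are in SAP 6.6.1 (general experience), 6.6.2 (EVH experience) and 6.6.3 (OVH experience). Each promises the rate of MACE and its components: "A separate table (similar to TABLE 21) will be provided for each level of experience". The Table 21 shell has Yes, No and Total columns with N and %, by arm. It has no person-time, survival estimate or fixed window, and 6.6 does not say whether the active or the entire follow-up period is meant.

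SAP 7.1 has the active period "begin with the first randomized patient and end after the last participant randomized has reached at least one-year of follow-up". On length it says: "Assuming the enrollment period is approximately three years", "this would equate to approximately 4 to 4.5 years of active follow-up". SAP 2.2.1 sets the floor: "A minimum of 1 year of active follow-up will be used for participants who will be randomized at the tail end". Table 22 gives mean follow-up by center and treatment, not by experience level.

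On late starts, Protocol XV.C allows centers to be dropped or added, and "back up sites with IRB approval will be identified prior to study initiation to minimize the delay in adding a new site".

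**The concern.** With one calendar close-out, the chance of having a recorded event depends on how long a patient was watched as well as on the hazard. Within a table the two arms share the same mix of entry dates, because allocation is blocked within harvester (SAP 3.4). Across tables nothing equalizes entry dates, and the comparison across experience levels is the one Objective 6 needs. If one level's patients came in later, its MACE percentage falls for that reason alone. If the less experienced harvesters were also the later ones, a real experience effect could be hidden or reversed, and no planned output shows follow-up by level to warn the reader.

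**Working it through.** **What the plan gives.** It states no figure for this effect. The anchor is its one-year planning rates, EVH 15.5% and OVH 9.5% (SAP 3.6), mean (15.5 + 9.5)/2 = 12.5%. These are the rates behind the stated sample size: [1.960·√(2·0.125·0.875) + 1.036·√(0.095·0.905 + 0.155·0.845)]² / 0.06² = 544.01, rounded up to the plan's 545 per group.

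**Follow-up range.** Three years of accrual plus at least one year gives about 1–4 years per patient (close-out at month 48). The Protocol's site budget agrees: after 36 months of recruitment it has "12 months F/U FY 17". Its 3 + 36 + 12 + 3 = 54 months include start-up and close-out. I also ran month 54 from first randomization, which implies 1.5–4.5 years.

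**Assumptions that are mine.** The hazard is the same for every harvester, 12.5% have MACE by one year, the hazard h afterwards is 0.03, 0.05 or 0.08 per year, and accrual is uniform.

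**Formula.** With follow-up uniform on a to b years (a ≥ 1):

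crude proportion = 1 − 0.875·[e^(−h(a−1)) − e^(−h(b−1))] / [h(b−a)]

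Example, h = 0.05, month 48:
- Whole accrual (1–4 years): 1 − 0.875·(1 − e^(−0.15))/0.15 = 18.7%.
- Start 12 months late (1–3 years): 1 − 0.875·(1 − e^(−0.10))/0.10 = 16.7%, which is 10.7% lower.
- Last year of accrual only (1–2 years): 1 − 0.875·(1 − e^(−0.05))/0.05 = 14.7%, which is 21.8% lower.

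| Close-out | h per year | Whole accrual | 12 months late (relative drop) | Last year only (relative drop) |
|---|---|---|---|---|
| Month 48 | 0.03 | 16.3% | 15.1% (7.7%) | 13.8% (15.5%) |
| Month 48 | 0.05 | 18.7% | 16.7% (10.7%) | 14.7% (21.8%) |
| Month 48 | 0.08 | 22.2% | 19.1% (13.8%) | 15.9% (28.4%) |
| Month 54 | 0.03 | 17.6% | 16.3% (7.0%) | 15.1% (14.1%) |
| Month 54 | 0.05 | 20.8% | 18.8% (9.5%) | 16.8% (19.2%) |
| Month 54 | 0.08 | 25.3% | 22.3% (11.7%) | 19.2% (24.0%) |

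A start 6 months late gives 3.5–6.8%.

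**Sensitivity to the hazard.**
- The Protocol's Introduction cites three-year rates of 20.2% and 17.4% from an earlier trial, midpoint 18.8%. Then h = ln(0.875/0.812)/2 = 0.037, and the month-48 drops are 8.9% and 18.1%.
- A constant hazard of −ln(0.875) = 0.1335 per year throughout gives 16.8% and 35.2% (1–4 years).
- Protocol XVII.B assumes MACE of 16.5% and 8.5% at about 4.5 years, mean 12.5%, the same as at one year. Read literally, no events occur after year 1 and the effect is zero. But 8.5% in OVH at 4.5 years is below 9.5% at one year, which a cumulative proportion cannot do, so these figures do not settle the hazard.

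**Candidate replacements.** The one-year Kaplan-Meier estimate is 12.5% whatever the start date, because every patient can reach one year. Events per person-time are not invariant here. Expected person-time is (1 − 0.875)/0.1335 + (crude − 0.125)/h. For h = 0.03 and month 48:
- Whole accrual: 0.936 + 0.0382/0.03 = 2.21 years, so 0.1632/2.21 = 7.39 per 100 person-years.
- Last year only: 0.936 + 0.0130/0.03 = 1.37 years, so 10.08 per 100 person-years.

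The late group now looks 36% worse. Over all six scenarios it looks about 8–36% worse. Person-time rates are free of start date only if the hazard is constant.

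**The case against.** The strongest reply is that the necessary premise is absent: levels are distorted against each other only if experience is related to enrollment date, and nothing in the documents says so. Adding centers is a contingency with no number or date, and SAP Table 2 lists 16 centers, the number planned. A reader might infer late starters from harvester codes that do not begin at 01 (Tucson 02; Milwaukee 03–05 in SAP Table 11). But codes carry no dates, and under Protocol Appendix F they go to qualified harvesters, including a designated open-only harvester, so a missing code may mean someone who took no randomized endoscopic case. This stands, and the point is therefore conditional.

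Second, SAP section 6 is descriptive, and SAP 7.1 has a Cox model that handles censoring and mentions harvester experience. This stands in part. Experience appears there only as an example of a covariate, SAP 7.3 sets out no analysis for Objective 6, and the model would not correct the 6.6 tables.

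Third, Table 22 would reveal uneven follow-up between centers. It would, but not between experience levels.

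Fourth, a one-year estimate drops later events in a trial about long-term outcome. That is true and is a cost of the change.

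**Conclusion.** The point holds as a conditional weakness of descriptive tables for an exploratory aim. The tables mix hazard with observation time and give the reader no means of separating them. Under the assumed hazards the relative difference is about 7–14% for a level starting 12 months late and 14–28% for one active only in the last year of accrual. A level mixing early and late harvesters would show less. These sizes rest on assumed event rates after year 1, which the documents do not fix.

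A reader might infer that late-starting harvesters will look 14–28% safer. The documents do not support that: they show no link between experience and start date, and the range belongs to the extreme case in which a whole level enrolls only in the final year. Nor is the EVH–OVH comparison within an experience level affected. Label: cheap improvement.

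**What to change.** In SAP 6.6.1–6.6.3:
- Replace the crude MACE percentage with the Kaplan-Meier estimate at one year and its 95% CI, by experience level and arm. A three-year estimate may be added with the number at risk, since late entrants will not reach three years of active follow-up.
- For the MI and revascularization components, give cumulative incidence at the same times with death as a competing event.
- Show median follow-up by experience level, and state that the active period is used.
- Do not use crude events per 100 person-years as the comparison across levels. With a front-loaded hazard they also depend on start date, in the opposite direction.

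The cost is a changed table shell. Event and censoring dates are already needed for SAP Figure 2, so no new data are collected. The downside is that the one-year estimate leaves out later events.

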6.6.3 MACE by OVH Experience

The rate of MACE and its components (all-cause mortality, nonfatal myocardial infarction, & repeat revascularization) will be reported by harvesters' OVH Experience: < 50, > 50 but < 100, > 100 but < 500, > 500 but < 1,000, >1,000 but < 2,000, and >2,000 endoscopic vein harvests completed. A separate table (similar to TABLE 21) will be provided for each level of experience.

6.7 Serious Adverse Events

Serious adverse event (SAE) incidence using MedDRA coding after randomization will be reported by body system and preferred term, overall and by treatment (TABLE 23).

6.8 Protocol Non-compliance

A listing of protocol non-compliance by medical center will be provided (TABLE 24).

7 STATISTICAL ANALYSES

7.1 Primary Outcome

The primary objective of this study is to investigate the impact of SVG harvesting techniques – OVH vs. EVH on MACE, a composite end point of all-cause mortality, nonfatal myocardial infarction and repeat revascularization, over the active follow-up period of the study postoperatively. The active follow-up time would begin with the first randomized patient and end after the last participant randomized has reached at least one-year of follow-up. Assuming the enrollment period is approximately three years, this would equate to approximately 4 to 4.5 years of active follow-up (in-clinic visit or contact by telephone carried out by site personnel), which will also be followed by two years of passive follow-up (carried out centrally by the chair's office staff using VA administrative databases). Thus, total follow-up time (active and passive) would be approximately 6.5 years. The primary outcome in the study is time (from index CABG surgery date) until the event of interest, MACE, or time-to-MACE during active follow-up (~4.5 years). Only the first event among participants will be considered as the MACE event.

To begin the analyses, the rate of MACE and its components (all-cause mortality, nonfatal myocardial infarction, & repeat revascularization) during active follow-up will be reported, both collectively and by SVG harvesting technique, OVH vs. EVH, considering only the first event so that components sum to total MACE (similar to TABLE 21). Survival analysis techniques will be employed to analyze the time-to-MACE data. Participants who are either lost-to-follow-up or did not experience a MACE event during the active follow-up period will be considered right-censored. Kaplan-Meier nonparametric survival estimates for risk of MACE will depict the unadjusted impact of SVG harvesting technique on MACE (FIGURE 2). Survival time represents time not experiencing a MACE. Tests of

equality (null hypothesis) of the survival function estimates across strata (OVH and EVH) will employ either the log-rank or Wilcoxon test. Multivariable survival analyses applying a Cox proportional hazards regression model will be performed to investigate the effect of SVG harvesting technique on time-to-MACE, adjusting for other potentially influential baseline characteristics, such as age, gender, harvester's experience, etc. (TABLE 25). Assumptions of the model (i.e., non-informative censoring, proportional hazards) will be checked. If assumptions appear to be violated, alternative methods will be explored (e.g., piecewise, time-varying covariates). A type I error rate of $\alpha = 0.05$ will be used throughout. Confidence intervals will be two-sided with a 95% confidence level.

The hypothesis for the primary aim of this study is:

H1: A significantly smaller proportion of CABG subjects with SVGs harvested by open technique will experience MACE post-surgery compared to CABG subjects with SVGs harvested by endoscopic technique during the active follow-up period.

The hypothesis for the primary aim of this study will be supported when an increased risk of MACE is observed among participants randomized to EVH, confirmed with a hazards ratio (HR) > 1.00 for EVH vs. OVH and a significant corresponding p -value $< \alpha$.

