All subjects will be followed up actively until the sites are decommissioned. After the six-week clinic visit, each subject will be contacted by phone, every three months, to collect information on any MACE event, leg wound status, etc. If the subject cannot be contacted, his/her CPRS records will be assessed to check for any MACE event. If the subject dies or refuses to continue participation, he/she will be terminated. A termination form will be used to record the termination information for these subjects. At the end of the active follow-up phase (approximately 4.5 years from study start-up) each continuing subject's status will be recorded in a termination form to indicate official termination of the active follow-up phase of the study.

All subjects terminated from the active follow-up phase of the study will be continually followed by the study's national nurse coordinator where existing VA administrative databases will be mined for MACE for another two years (passive follow-up phase).

XI. Quality Control Procedures

A. Standardization/Validation of Measurements

Prior to the start of the study enrollment, all of the site investigators, harvesters and research coordinators will be provided with in-depth trainings on different aspects of the conduct of the study during a “kick-off” meeting to ensure proper understanding of the technical aspects of the protocol, to ensure uniformity in the completion and submission of the case report forms and to ensure uniformity in implementing and performing the study procedures.

During this meeting, the site investigators and harvesters will receive a half-day of Good Clinical Practices (GCP) training and the research coordinators will receive one day of GCP training. If any of the research coordinators from the participating sites is unable to attend the kick-off meeting, a repeat GCP training will be arranged. The GCP trainings will be provided by the SMART team from the Pharmacy Coordinating Center, Albuquerque, New Mexico. In any event, until this training is completed, the sites will not be allowed to begin randomization for the study.

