6.5 Study Endpoint

The rate of MACE and its components (all-cause mortality, nonfatal myocardial infarction, & repeat revascularization) will be reported, overall and by treatment (TABLE 21). Mean length of follow-up (in days) will also be reported by medical center and treatment (TABLE 22).

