7.2 Secondary Outcomes

Secondary objectives of this study include investigating the impact of SVG harvesting techniques – OVH vs. EVH on MACE at one and three-years postoperatively and over the entire follow-up period (active and passive, ~ 6.5 years) of the study postoperatively. The proportion of participants experiencing a MACE (yes/no) in the first year of follow-up after index CABG surgery date will be calculated, both collectively and by SVG harvesting technique, OVH vs. EVH. These two proportions will be compared using Pearson's chi-square test. The proportion of participants experiencing a MACE (yes-1/no-0) in the three years of follow-up after index CABG surgery date will be similarly analyzed (TABLE 26).

Assessing MACE over the entire follow-up period (active and passive) of the study postoperatively will be analyzed similarly (TABLE 21, FIGURE 2, TABLE 25) to the primary outcome with now the outcome being time (from index CABG surgery date) until the event of interest, MACE, or time-to-MACE during the entire follow-up (~ 6.5 years). Events from both the active and passive follow-up periods will be considered, whereas the primary analysis only included events from the active follow-up period. Only the first event among participants will be considered as the MACE event.

The hypotheses for the secondary aims of this study are:

H2: One-year composite MACE rate will be 6 percentage points lower in the open harvesting group and three-year composite MACE rates will be at least 8-10 percentage points lower in the open vein harvesting group compared to the endoscopic vein harvesting group.

H3: A significant smaller proportion of CABG subjects with SVGs harvested by open technique will experience MACE post-surgery compared to CABG subjects with SVGs harvested by endoscopic technique during the entire follow-up period.

The hypothesis H2 will be supported when the percent of participants experiencing MACE at one-year is 6% and at least 8% greater at three-years among those randomized to EVH vs. OVH, with a significant corresponding *p*-value < α observed for each test. The hypothesis H3 will be supported when an increased risk of MACE is observed among participants randomized to EVH, confirmed with a hazards ratio (HR) > 1.00 for EVH vs. OVH and a significant corresponding *p*-value. A total (recurrent) event analysis at various time points will also be explored comparing EVH and OVH.

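### The SAP 7.1 and 7.2 component tables count only each patient's first event, so their all-cause mortality row omits deaths after a non-fatal MI or revascularisation, and no order-free component estimate is pre-specified

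*SAP*

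**What the plan says.** SAP 7.1 opens the primary analysis with a table of MACE and its components (all-cause mortality, non-fatal MI, repeat revascularisation) over active follow-up, by arm, "considering only the first event so that components sum to total MACE". It describes this table as similar to Table 21. For the composite it adds: "Only the first event among participants will be considered as the MACE event".

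SAP 7.2 says that MACE over the entire follow-up "will be analyzed similarly (TABLE 21, FIGURE 2, TABLE 25) to the primary outcome". On its natural reading, this brings the same component rule with it.

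Other places give no such rule for components:

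- SAP 6.5: "The rate of MACE and its components (all-cause mortality, nonfatal myocardial infarction, & repeat revascularization) will be reported, overall and by treatment", in Table 21, which has separate yes/no rows for death, MI and repeat revascularisation.
- SAP Table 26 lists death, MI and revascularisation by arm at one and three years, with component p-values dashed out.
- Protocol Appendix D, Tables 10-12 and 14-16, are separate yes/no tables by arm, each with a chi-square test. Two of them are for all-cause death.

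SAP 7.2 also has one sentence on repeated events: "A total (recurrent) event analysis at various time points will also be explored comparing EVH and OVH". It names no method and no time points.

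**The concern.** First-event counting is right for the composite. Applied to the components, it answers a different question: which kind of event came first. A row headed all-cause mortality will be read as deaths by arm, and under this rule it is not.

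The label matters in this trial. The suspected harm of EVH is graft failure. The protocol's background reports that, after graft failure, the composite was driven by repeat revascularisation, a non-fatal event. A patient who is revascularised and then dies would sit under revascularisation only. Such deaths accumulate with time, so the 6.5-year table in 7.2 is the more exposed of the two. The protocol's background also gives 3-year mortality by harvest technique as a main result of the registry study it cites, so readers will look for that comparison here.

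**Working it through.** **1. The plan's own figures, and whether they depend on this.** SAP 3.6 gives 545 per group for 15.5% against 9.5%, 85% power, two-sided 5%. With pooled variance and no continuity correction:

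n = [1.960·√(2·0.125·0.875) + 1.036·√(0.095·0.905 + 0.155·0.845)]² / 0.06² = (0.9167 + 0.4827)² / 0.0036 ≈ 544.01, rounded up to 545. This reproduces the plan.

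Protocol XVII.B gives 532 per group and 97.5% power for event-free rates of 83.5% and 91.5%. HR = ln 0.835 / ln 0.915 = 2.03. Expected events = 532 × (0.165 + 0.085) = 133. By Freedman's formula, z = √133 × (1.03/3.03) − 1.96 = 1.96, so power is 97.5%. This also reproduces.

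Both calculations use the composite. How the components are tabulated enters neither.

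**2. How often component types overlap.** The only data in the documents are in Protocol Table 1 (ROOBY, one year). If non-fatal MI and revascularisation are both in that composite, the number of patients with both is at least MI + revascularisation − composite.

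| ROOBY group | MI | Revasc. | Sum | Composite patients | Minimum overlap |
|---|---|---|---|---|---|
| One or more territories ineffectively revascularised | 60 | 54 | 114 | 96 | 18 |
| All territories effectively revascularised | 33 | 14 | 47 | 46 | 1 |
| Both | 93 | 68 | 161 | 142 | 19 |

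A first-event table has at most one entry per composite patient. It would therefore drop at least 19 of 161 occurrences (11.8%). This is a lower bound: any composite patient who had only a death raises it.

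**3. Later deaths.** These cannot be derived from the documents, so the following is an illustration on assumed inputs. Take 575 per arm (1150/2) and the protocol's MACE proportions of 16.5% and 8.5%. Assume that 50-70% of first events are non-fatal and that 5-20% of those patients die later in follow-up.

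- EVH: 575 × 0.165 × 0.5 × 0.05 = 2.4, up to 575 × 0.165 × 0.7 × 0.20 = 13.3 deaths left out.
- OVH: 575 × 0.085 × 0.5 × 0.05 = 1.2, up to 575 × 0.085 × 0.7 × 0.20 = 6.8 deaths left out.
- As a share of all deaths among MACE patients: 0.025/(0.025 + 0.5) = 4.8%, up to 0.14/(0.14 + 0.3) = 31.8%.

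The share is the same in both arms because the same proportions were assumed in both. The larger EVH count comes only from the planning MACE rates.

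**4. Whether the data exist.** Protocol X.E: "All subjects will be followed up actively until the sites are decommissioned". The six-week and telephone forms (Forms 11 and 12) ask about death, MI, PCI and CABG since the last contact. The Clinical Events Committee reviews all study deaths (Protocol XV.A). Events after a first non-fatal event are therefore collected.

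**The case against.** The strongest reply is that the plan contains two displays: full counts in 6.5 with Table 21, and a type-of-first-event variant in 7.1, which is only said to be similar to Table 21. The 7.1 table is descriptive. The inferential comparison is time to first MACE, where a patient with an MI who later dies already counts, at the earlier date. Serious adverse events are summarised by arm, and a recurrent-event analysis is foreseen.

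Much of this stands, and it rules out several stronger readings that a reader might infer:

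- *That the SAP as a whole counts components only as first events.* The rule is stated in 7.1 and carried over by 7.2. SAP 6.5, Table 26 and the protocol's component tables do not state it.
- *That 7.1 overrides 6.5 through SAP 5.4.* Section 5.4 lets specific sections prevail over its own list of general policies (rounding, sorting, partial dates, software). It does not rank 7.1 above 6.5, which is itself a specific section.
- *That later events vanish from every arm comparison.* Tables 21 and 26 could be programmed as full counts.
- *That the loss is uneven and hides harm from EVH.* The ROOBY columns are groups by graft effectiveness, not harvest arms, and the table has no death row. The 18-against-1 split says nothing about EVH against OVH.

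The reply does not supply a counting rule for Tables 21 and 26, a correct label for the 7.1 and 7.2 tables, or a defined analysis of death. An adverse-event summary by body system and preferred term is not a mortality comparison, and an analysis that is merely to be explored is not pre-specified.

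**Conclusion.** The point holds in a limited form. The only component rule that the SAP states yields a mortality row that is not all-cause mortality, and MI and revascularisation rows that omit second event types. The counting rule elsewhere is open, and no by-arm effect estimate for death, or for each component regardless of order, is pre-specified.

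The primary test, the 545 per group and the 97.5% power do not change. The documented size is overlap of at least 19 of 161 MI and revascularisation occurrences at one year in ROOBY. That assumes both belong to its composite, whose footnote is not shown. The range for missing deaths (about 2-13 EVH and 1-7 OVH) rests wholly on assumed proportions. Differential loss by arm remains a possibility to guard against, not a finding.

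**What to change.** 1. In SAP 7.1 and 7.2, keep the additive table if it is wanted, but label it 'type of first event' and do not head its death row all-cause mortality.
2. State that Tables 21 and 26 count every patient with each component regardless of earlier events: all deaths, any MI, any revascularisation.
3. Pre-specify, as supportive analyses, time to first occurrence of each component, with a hazard ratio and 95% CI by arm. For MI and revascularisation add cumulative incidence with death as a competing event.
4. Leave first-event counting for the composite as it is.

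The cost is SAP wording and a few more table rows, with no new data collection and no change in sample size. The downside is that component rows in Tables 21 and 26 will no longer sum to total MACE, which a footnote should say.
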